## **12.3 Efficacy Assessment**

### **12.3.1 Definition of response**

Lesions will be separately tracked but response determined in totality. As indicated, patient must have at least one trackable lesion by response evaluation criteria in solid tumors (RECIST) 1.1. Response will be defined as best overall response by RECIST 1.1 of complete or partial response.

### **12.3.2 Definition of success and power of success**

Responses to alternative therapies in this population of patients with advanced TNBC/urothelial carcinoma/NSCLC resistant to PD-1/PD-L1 axis blockade are rare, and we therefore will use a 5% response rate as the fixed benchmark upon which we hope to improve with the proposed treatment. If the true response rate with TCR-transduced cells is 25%, 15 patients yields 84% power to detect a statistically significantly improved response rate (one-sided .05) over the fixed rate of 5%. Three or more responses among 16 pts would occur with probability .04 if the true response rate is 5%, so if three or more patients respond (an observed response rate of at least 19%), we will conclude that this regimen is potentially efficacious and worthy of further study.

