## 12.0 STATISTICAL CONSIDERATIONS

### 12.1 Type of Study

Our study is a phase I/II, non-blinded interventional trial. Our target sample size is 15-18 patients (8-12 per year/1.5-2 years). This enrollment target is chosen for three reasons: it is achievable from an enrollment standpoint (our clinic sees hundreds of metastatic TNBC, urothelial or NSCLC patients potentially eligible per year), it is logistically possible from a funding and cell processing facility standpoint, and it allows >80% power to observe a statistically significant (at one-sided 0.05 level) efficacy signal that is clinically meaningful (see below). Patients will be treated at three potential dose levels (from  $1 \times 10^9$  up to  $5 \times 10^9$  TCR-MagIC transgenic CD3+).

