## **12.5 Sample Size and Accrual**

This study is a phase I, non-blinded interventional trial. Our target sample size is 15-18 patients (8-12 per year/1.5-2 years).

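### Power at 15 patients is 76%, not the stated 84%, and the success rule of three responders (at least 19%) is not consistent across the 15-18 target

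*Combined protocol and SAP*

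**What the plan says.** Section 12.3.2 defines success on RECIST 1.1 response. For the null rate it says "we therefore will use a 5% response rate as the fixed benchmark". For the alternative it says "If the true response rate with TCR-transduced cells is 25"%, and at that rate "15 patients yields 84% power to detect a statistically significantly improved response rate (one-sided .05) over the fixed rate of 5"%.

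It then moves to a different sample size: "Three or more responses among 16 pts would occur with probability .04 if the true response rate is 5"%. From this calculation it derives the success rule: "so if three or more patients respond (an observed response rate of at least 19%), we will conclude that this regimen is potentially efficacious".

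Section 12.1 gives power as one of three reasons for the enrolment target: "it allows >80% power to observe a statistically significant (at one-sided 0.05 level) efficacy signal that is clinically meaningful". Sections 12.1 and 12.5 both set that target as a range: "Our target sample size is 15-18 patients (8-12 per year/1.5-2 years"). No statistical test is named, and no critical count is given for any sample size other than 16.

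**The concern.** Power is quoted at 15 patients, type I error at 16, and the target runs from 15 to 18. With counts this small, one patient more or less changes both error rates noticeably, so figures for different sample sizes cannot be combined into one design statement.

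Two things are at stake. First, readers are told that 15 patients carry a 16% risk of missing a true 25% response rate. If that risk is larger, the stated justification for the low end of the target fails. Second, the efficacy conclusion turns on about three responders. If the count and the percentage can point in opposite directions at a planned sample size, the choice between them would be made after the result is known.

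**Working it through.** **Inputs (12.1, 12.3.2, 12.5).** Null rate 5%, alternative 25%, one-sided 0.05, binary endpoint, n from 15 to 18.

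**Formula.** For X ~ Binomial(n, p), P(X ≥ r) = 1 − Σ C(n, x) pˣ (1 − p)ⁿ⁻ˣ, summed over x = 0 to r − 1. Type I error uses p = 0.05 and power uses p = 0.25.

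**Step 1: the plan's own type I error (n = 16, r = 3).** P(0) = 0.44013, P(1) = 0.37063 and P(2) = 0.14630, which sum to 0.95706. The tail is 1 − 0.95706 = 0.0429, which rounds to the plan's .04. Mid-p gives 0.025 and the uncorrected score test 0.006. The plan's figure is therefore the exact binomial tail.

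**Step 2: critical count at n = 15.** Under 5%, P(0) = 0.46329, P(1) = 0.36576 and P(2) = 0.13475.
- P(X ≥ 2) = 1 − 0.82905 = 0.171, not significant.
- P(X ≥ 3) = 1 − 0.96380 = 0.036, significant.

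The cut-off is 3.

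**Step 3: power at n = 15.** Under 25%, P(0) = 0.01336, P(1) = 0.06682 and P(2) = 0.15591, which sum to 0.23609. Power is 1 − 0.23609 = 0.7639, or 76.4%. The stated 84% is too high by 7.6 points.

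**Step 4: would another test give 84%?** For 2/15, mid-p is 0.0362 + 0.13475/2 = 0.104. The uncorrected score test has z = (0.1333 − 0.05)/√(0.05 × 0.95/15) = 1.48, p = 0.069. Both leave the cut-off at 3 and power at 76.4%. A Wald test needs 4 responders, with power 53.9%. Even a randomized most powerful test of size exactly 0.05 reaches only 78.0%.

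The uncorrected normal approximation does come close:
- Cut-off: 15 × [0.05 + 1.645 × √(0.05 × 0.95/15)] = 2.14 responders.
- Power: Φ[(0.25 − 0.1426)/√(0.25 × 0.75/15)] = 83.2%.

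A cut-off of 2.14 cannot be observed. Rounded up to 3 it gives 76.4%. The expected number of responders under the null is only 15 × 0.05 = 0.75, too few for a normal approximation.

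**Step 5: the rule across the target range.**

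| n | 3/n | Type I error, 3 or more | Power, 3 or more | Type I error, 4 or more | Power, 4 or more |
|---|---|---|---|---|---|
| 15 | 20.0% | 0.0362 | 76.4% | 0.0055 | 53.9% |
| 16 | 18.75% | 0.0429 | 80.3% | 0.0070 | 59.5% |
| 17 | 17.6% | 0.0503 | 83.6% | 0.0088 | 64.7% |
| 18 | 16.7% | 0.0581 | 86.5% | 0.0109 | 69.4% |

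Reading 19% as 3/16, a percentage threshold requires 4 responders at n = 17 and 18. The two readings conflict when exactly 3 patients respond. At a true rate of 25%, that has probability 0.8363 − 0.6470 = 18.9% at n = 17 and 0.8647 − 0.6943 = 17.0% at n = 18.

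**Step 6: what 84% would require at n = 15.** With a cut-off of 3, power reaches 80% at a true response rate of 26.4% and 84% at 28.2%.

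**The case against.** Four points can be made for the plan.

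*The 19% is only a gloss.* The rule follows directly from the calculation for 16 patients, and the percentage is 3/16 rounded. Taken literally, 19% would reject 3/16 itself (18.75%), so it was hardly meant as a separate threshold. This largely stands: the count is the natural criterion, and the 18.9% and 17.0% conflict probabilities matter only on the less natural reading. But the sentence is not limited to 16 patients while the target is a range, and if the count governs, the type I error at 18 exceeds the declared level.

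*If the count governs, the damage is modest.* Power exceeds 80% at 16, 17 and 18 and falls short at 15 by 3.6 points. A type I error of 0.0503 at 17 is .05 at the plan's precision, and 0.058 at 18 is a small excess. This stands as a statement of size. It does not make 84% correct for 15 patients.

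*The figure may be a legitimate approximation.* It may come from the normal approximation (83.2% at 15) or from a mismatched sample size (exact power at 17 is 83.6%). The documents do not say which. Neither origin gives the rule 84% power at 15 patients.

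*This is a small early-phase trial.* Power is one of three reasons for the sample size, and success means only that further study is warranted. That limits the consequences. Still, 12.3.2 states a significance level, a power and a firm conclusion, and these should be right.

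**Conclusion.** The plan is wrong as written. Exact power at 15 patients is 76.4% against a stated 84%, so the risk of missing a true 25% response rate is 24% rather than 16%. The claim in 12.1 of more than 80% power fails at 15 and holds at 16 to 18 if three responders is the criterion throughout.

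Of the four sample sizes, only 16 strictly meets both a type I error of at most 0.05 and power above 80% with an exact test (0.043, 80.3%). If 0.0503 is accepted as .05, 17 qualifies too. At 18 the three-responder rule has a type I error of 0.058.

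The mismatch between count and percentage at 17 and 18 is the lesser part: probably unintended, but present in the text.

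These results rest on the plan's rates of 5% and 25%, independent patients, and one analysis at the final sample size. The 76.4% is the same under the exact, mid-p and uncorrected score tests. The Wald test gives less.

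**What to change.** Make these changes before response data are seen.

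- **12.3.2, power.** Replace the power statement with: *15 patients yield 76% power and 16 patients yield 80% power (exact binomial, one-sided .05, three or more responses).*
- **12.1.** Tie the claim of more than 80% power to 16 patients, or qualify it to say that it does not hold at 15.
- **12.3.2, rule.** Name the exact binomial test and tabulate one critical count, with exact type I error and power, for each sample size from 15 to 18. Remove the 19%, or state that it applies only to 16 patients.

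The simplest consistent rule keeps three responders at every sample size: type I error 0.036, 0.043, 0.050 and 0.058, and power 76%, 80%, 84% and 86%, for n = 15 to 18, with the 0.058 acknowledged. The alternative is three responders at 15-16 and four at 17-18. It holds the type I error below 0.05 throughout, but it changes the success criterion and cuts power to 65% and 69% at 17 and 18. Naming 16 as the efficacy analysis size is a further option.

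Keeping the count of three costs only wording in 12.1 and 12.3.2, with no extra patients and no change in conduct. The price is a less favourable stated power and a decision, made in advance, between a slightly raised type I error at 18 and lower power at 17-18.

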## **12.4 Secondary and exploratory analyses**

Progression free and overall survival will be estimated using the method of Kaplan and Meier, with time zero the time of first T cell infusion. Given the small size of the trial, many of the secondary and exploratory endpoints are descriptive or hypothesis generating in nature, and are thus underpowered for formal statistical analysis. Standard methods will be used to estimate each of the secondary endpoints.

## **12.5 Sample Size and Accrual**

This study is a phase I, non-blinded interventional trial. Our target sample size is 15-18 patients (8-12 per year/1.5-2 years).

## **13.0 DATA AND SAFETY MONITORING PLAN**

### **13.1 Overall Scope of Monitoring Activities**

Institutional support of trial monitoring will be in accordance with the Fred Hutch/University of Washington Cancer Consortium Institutional Data and Safety Monitoring Plan (DSMP). Under the provisions of this plan, Fred Hutch Clinical Research Support coordinates data and compliance monitoring conducted by consultants, contract research organizations, or Fred Hutch employees unaffiliated with the conduct of the study. Independent monitoring visits occur at specified intervals determined by the assessed risk level of the study and the findings of previous visits per the institutional DSMP.

In addition, protocols are reviewed at least annually and as needed by the Consortium Data and Safety Monitoring Committee (DSMC), Fred Hutch Scientific Review Committee (SRC) and the Fred Hutch/University of Washington Cancer Consortium Institutional Review Board (IRB). The review committees evaluate accrual, adverse events, stopping rules, and adherence to the applicable data and safety monitoring plan for studies actively enrolling or treating patients. The IRB reviews the study

progress and safety information to assess continued acceptability of the risk-benefit ratio for human patients. Approval of committees as applicable is necessary to continue the study.

The trial will comply with the standard guidelines set forth by these regulatory committees and other institutional, state and federal guidelines. The conduct of this trial will be further monitored by an independent Data and Safety Monitoring Board (DSMB) in accordance with an approved DSMB Charter.

### **13.2 Monitoring the Progress of Trial and Safety of Participants**

The first level of trial oversight for this protocol will be provided by the Principal Investigator, the Research Nurse, and Research Coordinator(s), who will provide continuous oversight of the trial. These individuals will meet at least monthly to review recently acquired data, stopping rules, and adverse events. Serious adverse events will be reviewed upon occurrence to ensure prompt and accurate reporting to the IND Sponsor, appropriate committees, and regulatory agencies as described above. The data recorded in the research charts and protocol database will be compared with the actual data available from the medical record and/or clinical histories. Data detailed in the research case report forms (CRFs) will include the nature and severity of all grade 3-5 adverse events. The Principal Investigator and all other investigators on the protocol have received formal training in the ethical conduct of human research.

The IND Sponsor will ensure routine trial monitoring as described above, and will review Serious Adverse Events and other reports of safety issues promptly upon receipt from the PI.

A DSMB will be in place and will meet after all patients in a given dose level have received treatment (or sooner if requested) to review the data as it relates to AEs and determine whether trial may proceed to phase II dose level. The purpose of the DSMB meetings is to review the conduct of the trial to date and assess safety and toxicity of the study intervention. The DSMB will review all grade 3 or greater NIH CTC v5.0 toxicities and SAEs and determine whether the study should be prematurely discontinued due to excessive toxicity consistent with **Section 13**. Ad hoc meetings may be scheduled as needed.

### **14.0 DATA MANAGEMENT/CONFIDENTIALITY**

The medical record containing information regarding treatment of the patient will be maintained as a confidential document, within the guidelines of the Fred Hutchinson Cancer Research Center, the University of Washington Medical Center, and the Seattle Cancer Care Alliance.

The investigator will ensure that data collected conform to all established guidelines for coding collection, key entry and verification. Each patient is assigned a unique patient number to assure patient confidentiality. Information forwarded to the FDA, NIH, NCI or other agencies about patients on this protocol refers to patients by a coded identifier and not by name. Patients will not be referred to by this number, by name, or by any other individual identifier in any publication or external presentation. The licensed medical records department, affiliated with the institution where the

patient receives medical care, maintains all original inpatient and outpatient chart documents. Additional clinical data may be made available from the Fred Hutch core database which is managed and verified independent of the research group.

The research team will maintain Case Report Forms (CRFs) and associated research documentation for each patient treated under the protocol. This documentation includes both clinical data and study-specific documents for each patient. The Principal Investigator or a designee will verify completed CRFs against source documentation on an ongoing basis as they are completed for individual patients. Data required for analysis of patients treated on this protocol will be maintained in a password-protected study-specific database. Data from the CRFs are keyed directly into the database by authorized research staff and verified on an ongoing basis.

## **15.0 TERMINATION OF STUDY**

The study will terminate after the last treated patient has completed 15 years of follow-up as described in this protocol.

The PI or IND Sponsor may terminate the study at any time. The IRB and FDA also have the authority to terminate the study should it be deemed necessary.

### APPENDIX A: Schedule of Evaluations

Assessment	Screening	Pretreatment Evaluation	Lymphodepleting Chemotherapy (Day -4 to -2)	T cell Infusion (Day 0)							*see Note
					1	3	7	14	21	28	
Window		-30 days of leuka		Up to 7 days post-LD chemo	+/- 1 d	+/- 1 d	+/- 1 d	+/- 3 d	+/- 3 d	+/- 3 d	Day 60 +/- 14 days, Day 90-365 +/- 30 days
Informed consent/HIPAA	X	X									
HLA typing	X a										
MAGE A1 evaluation	X										
I/E criteria		X									
Medical history a	X				X		X	X	X	X	
Physical exam	X	X	X	X		X	X	X	X	X	
Height/weight b	X		X								
ECOG performance status	X	X	X								
Pregnancy test	X			X b							
Vitals including O 2 sat				X c							
Brain imaging b	X										
12-lead ECG	X										
MUGA/ECHO d		X									

RG1007463  
IR10420

Assessment	Screening	Pretreatment Evaluation	Lymphodepleting Chemotherapy (Day -4 to -2)	T cell Infusion (Day 0)	*see Note						
					1	3	7	14	21	28	
Window	-30 days of leuka		Up to 7 days post-LD chemo		+/- 1 d	+/- 1 d	+/- 1 d	+/- 3 d	+/- 3 d	+/- 3 d	
											Day 60 +/- 14 days, Day 90-365 +/- 30 days
CT/PET scan i		X									Performed at the following timepoints if clinically indicated or suspicion of progression: 
 
• Approximately 1 month after each T cell infusion
 
• Approximately 3 months after each T cell infusion
 
• Approximately 6 months after the last T cell infusion
 
• Approximately 9 months after the last T cell infusion
 
• Approximately 12 months after the last T cell infusion
 
 Before the patient receives additional antitumor therapy
Tumor biopsy (in subjects with accessible disease)		X						X			Performed at week 12 after each infusion then as clinically indicated.,
Leukapheresis		X									
Lymphodepleting chemotherapy			X								
T cell admin				X							
AEs		X	X	X	X	X	X	X	X	X	X
Neurological exam		X									

RG1007463  
IR10420

Assessment	Screening	Pretreatment Evaluation	Lymphodepleting Chemotherapy (Day -4 to -2)	T cell Infusion (Day 0)	*see Note							
					1	3	7	14	21	28		
Window	-30 days of leuka		Up to 7 days post-LD chemo	+/- 1 d	+/- 1 d	+/- 1 d	+/- 3 d	+/- 3 d	+/- 3 d			Day 60 +/- 14 days, Day 90-365 +/- 30 days
CBC, differential, platelet count	X	X	X	X	X	X	X	X	X	X		Concurrent with restaging as clinically indicated Concurrent with T-cell persistence evaluation
Renal, hepatic function with LDH, Mg	X	X	X	X	X	X	X	X	X	X		Concurrent with restaging as clinically indicated
Uric acid	X		X	X	X	X						
Serum ferritin	X											As clinically indicated
CRP	X											As clinically indicated
IL-6	X											As clinically indicated
DIC panel without platelets	X											As clinically indicated
Quantitative IgG f	X											Approximately monthly
Virology panel	X											
ABO blood typing; antibody screen	X											
G6PD screening	X											
T cell persistence	X	X			X	X	X	X	X	X		Approx. 6 weeks and 2, 3, 6, 9, and 12 months after the T cell infusion and at the time of tumor relapse
T cell cellular immune response		X								X		Approx 2, 3, 6, 9 and 12 months after the T cell infusion

RG1007463  
IR10420

Assessment	Screening	Pretreatment Evaluation	Lymphodepleting Chemotherapy (Day -4 to -2)	T cell Infusion (Day 0)	*see Note							
					1	3	7	14	21	28		
Window	-30 days of leuka		Up to 7 days post-LD chemo		+/- 1 d	+/- 1 d	+/- 1 d	+/- 3 d	+/- 3 d	+/- 3 d		
												Day 60 +/- 14 days, Day 90-365 +/- 30 days
RCL testing by VSVG qPCR	X											Approximately 3, 6, and 12 months after the last T cell infusion
Serum archive	X	X			X	X	X	X	X	X		Approximately at 3, 6, 9 and 12 months after the last T cell infusion
Citrate plasma archive	X	X			X	X	X	X	X	X		Approximately at 3, 6, 9 and 12 months after the last T cell infusion
Tumor Biopsy	X							X				Prior to enrollment, 2 weeks after and 12 weeks after the first T cell infusion.

\*NOTE: Protocol time points represent guidelines for performance of required evaluations. Due to numerous factors influencing scheduling (subject and provider availability, testing services limitations, etc.), variation in evaluation performance dates is anticipated and acceptable to the protocol (i.e., within  $\pm$  4 days of time points < day 30;  $\pm$  30 days for timepoints > day 30). Evaluations do not need to be repeated if results from previous test are available and within protocol window

a Medical history to include hematologic, cytogenetic, flow cytometric, and histologic findings at diagnosis and time of enrollment as well as prior therapies and response to therapy.

b Height required only at Pretreatment Evaluation.

c Vital signs and O2 saturation being recorded before, approximately **every 15 minutes during**, at completion of the infusion, and hourly after the infusion for at least 2 hours after infusion.

d ECHO required if patients  $\geq$ 60 years of age within 60 days of enrollment.

e Diagnostic CT/PET scan to include neck, chest, abdomen and pelvis, as clinically indicated by disease.

f In patient who receive lymphodepleting chemotherapy, quantitative IgG to be measured approximately monthly until levels are normal without IVIG replacement. If levels are still abnormal at the end of follow-up, IgG should continue to be assessed by the treating physician.

g Pregnancy test within 72 hours of cell infusion

RG1007463  
IR10420

- b If history of brain metastasis or neurologic symptoms
- i Repeat imaging if not within 45 days of infusion day

## APPENDIX B: Research Sample Checklist

Please note that many of the listed research studies are optional pending clinical course, and may be replaced by newer or alternate assays that answer the same general question. Note that the selected studies will be batched and results are not anticipated to be available in “real-time”. Leftover materials from all time points may be archived.

### RECIPIENT RESEARCH EVALUATIONS BEFORE T CELL INFUSION

SAMPLE	TIME	TEST	TUBE	VOL. (Approx)	LAB
Blood	At Enrollment	T cell persistence and functional studies, epitope spreading, scRNAseq, clonality	Lavender top	60 mL	Research Cell Bank (RCB)
Blood	At Enrollment	Cytokine levels	Serum separator	20 ml	RCB
Blood	At Enrollment	RCL Testing	Lavender top	10 ml	RCB
Tumor	At Enrollment	Single cell RNA sequencing	RPMI	3 cores	[name] D3-235
Tumor	At Enrollment	T cell localization and tumor microenvironment characteristics	Formalin	1 core; in addition to clinical core	[name] D3-235
Blood	Within 2 days prior to LD (or cell infusion if not receiving LD)	Cytokine levels (research)	Serum separator	10 ml	RCB
Blood	Within 2 days prior to LD (or cell infusion if not receiving LD)	T cell baseline persistence, function	Lavender top	30 ml	RCB

**RECIPIENT RESEARCH EVALUATIONS AFTER T CELL INFUSION**

SAMPLE	TIME	TEST	TUBE	VOL. (Approx)	LAB
Blood	Day 1	Cytokine levels (research)	Serum separator	20 ml	RCB
Blood	Day 1	T cell persistence, phenotype	Lavender top	60 ml	RCB
Blood	Day 3	Cytokine levels (research)	Serum separator	20 ml	RCB
Blood	Day 3	T cell persistence	Lavender top	60 ml	RCB
Blood	Day 7	Cytokine levels (research)	Serum separator	20 ml	RCB
Blood	Day 7	T cell persistence	Lavender top)	60 ml	RCB
Blood	Day 14	Cytokine levels (research)	Serum separator	20 ml	RCB
Blood	Day 14	T cell persistence and functional studies, epitope spreading, scRNAseq, clonality	Lavender top	60 ml	RCB
Blood	Day 21	Cytokine levels (research)	Serum separator	20 ml	RCB
Blood	Day 21	T cell persistence	Lavender top	60 ml	RCB
Blood	Day 28	Cytokine levels (research)	Serum separator	20 ml	RCB
Blood	Day 28	T cell persistence, immunophenotype	Lavender top	60 ml	RCB
Blood	Day 56	Cytokine levels (research)	Serum separator	20 ml	RCB
Blood	Day 56	T cell persistence, immunophenotype	Lavender top	60 ml	RCB
Blood	Day 84	T cell persistence, epitope spreading, scRNAseq, immunophenotype, clonality, RCL	Lavender top	60 ml	RCB
Blood	Day 84	Cytokines, research serologies	Serum separator	20 ml	RCB
If second infusion, repeat pattern above/please refer to study schedule					

SAMPLE	TIME	TEST	TUBE	VOL. (Approx)	LAB
Blood	Day 180	T cell persistence, epitope spreading, immunophenotype, clonality, RCL	Lavender top	60 ml	RCB
Blood	Day 180	Cytokines, research serologies	Serum separator	20 ml	RCB
Blood	Day 270	T cell persistence, epitope spreading, immunophenotype, clonality, RCL	Lavender top	60 ml	RCB
Blood	Day 270	Cytokines, research serologies	Serum separator	20 ml	RCB
Blood	Day 365	T cell persistence, epitope spreading, immunophenotype, clonality, RCL	Lavender top	60 ml	RCB
Blood	Day 365	Cytokines, research serologies	Serum separator	20 ml	RCB
Blood	Annual years 2-15	T cell persistence, RCL	Lavender top	20 ml	RCB
<hr/>					
Blood	Clinical events	T cell persistence, epitope spreading, immunophenotype, clonality, RCL, scRNAseq (all optional/TBD)	Lavender top	Up to 60 ml	Discuss with study staff
Blood	Clinical events	Cytokine levels	Serum separator	20 mL	Discuss with study staff
<hr/>					
Tumor	Day + 14	Single cell RNA sequencing	RPMI	3 cores or equiv	[name] D3-235
Tumor	Day + 14	T cell localization and tumor microenvironment characteristics	Formalin	1 core or equiv	[name] D3-235
Tumor	Day +14	Archive	RPMI	Any add'l tissue	[name] D3-235
Tumor	Day + 84	Single cell RNA sequencing	RPMI	3 cores or equiv	[name] D3-235

SAMPLE	TIME	TEST	TUBE	VOL. (Approx)	LAB
Tumor	Day + 84	T cell localization and tumor microenvironment characteristics	Formalin	1 core or equiv; in addition to clinical core(s)	[name] D3-235
Tumor	Day + 84	Archive	RPMI	Any add'l tissue	[name] D3-235
Tumor	Clinical event	Single cell RNA sequencing	RPMI	3 cores	[name] D3-235
Tumor	Clinical event	T cell localization and tumor microenvironment characteristics	Formalin	1 core; in addition to clinical core	[name] D3-235

